10. The Investigator informs the patient they have to visit the investigator before the next scheduled personal visit in case they do not have sufficient strips. Also, the patient can visit the investigator personally instead of the phone visit if the patient realizes they do not have enough strips to cover the period until the next scheduled personal visit. In this case, the patients have to bring the diary and his BGM for the visit and the Investigator will download the data from BGM and return it back to the patient. The diary will be kept by the investigator and the patient will receive the new diary. The patient also will receive the required number of strips in amount enough to the next scheduled personal visit.

Visit № 5 – study completion visit (personal).

1. The final patient examination is conducted by the physician-investigator, and, during this visit, the patient will be asked several questions, of which the answers are documented in the eCRF.
2. The physician-investigator enters the latest results of the glycated hemoglobin (HbA1c) measurements and insulin TDD (basal and boluses, of the day prior to the visit) in the patient's eCRF.
3. The data, saved in the patients' BGMs should be downloaded by the investigator. The downloaded data will be transmitted to the Sponsor for analysis. The data will be transferred for analysis and storage to Becton, Dickinson and Company in the United States of America.
4. The BGM must be returned to the site and transferred to the Sponsor.
5. The existing level of glycemic control and cases of hypoglycemia are assessed.
6. The physician conducts an examination of the injection sites and the injection technique, the size and localization of lipohypertrophy (if present).
7. The physician will review and collect the subject diaries.
8. Patients are requested to complete the EQ-5D questionnaire,
9. Data regarding possible AEs is collected in a special form of the patient's eCRF. If necessary, a subsequent medical follow-up is arranged for the patient.
10. The patient's exit from the study form is filled in.

Table 2 Calendar of events

Period	Screening	Follow-up		Study completion
Visit	1	2 and 4	3	5
Actions				
Informed consent	X			
Co-morbidities and medical history, demographic data	X			
Pregnancy urine test for female patients in childbearing age	X			
Inclusion/exclusion criteria	X			
Setting the dates for subsequent visits	X		X	
Setting the dates for blood HbA1c tests	X		X	
Patient questionnaire	X	X	X	X
Quality of Life questionnaire (EQ-5D)	X			X
Patient examination for lipohypertrophy	X		X	X
Glycated hemoglobin (HbA1c)	X		X	X
Collect information on occurrences of hypoglycemia	X	X	X	X
Patient education classes, video lessons scheduling, provision of needles	X			
Control of video lessons' viewing	X	X	X	X
Exit from the study				X
Collection of adverse event information		X	X	X

7.6. Patient training of correct injection technique

At the beginning of the trial, the physician interviews the patient in order to evaluate the existing injection technique. The gaps and downsides found are sorted out for each patient in terms of the correct injection technique practice, as set forth in the Russian Procedural Guidelines on injection techniques and infusions used in the treatment of diabetes mellitus [1] and in the international guidelines FITTER [5]. The physician-investigator recommends that patients view the video lessons which best suit their specific needs. Video lessons highlight the following topics:

1. How to deliver an injection with an insulin pen
2. Insulin delivery to the right place/injection sites
3. Using the right length of needles
4. Injection site swelling or induration
5. Injection site care

6. Insulin is absorbed differently by your body
7. Injections, possible problems and their solutions, idiopathic hypoglycemia and blood glucose spikes.
8. How to store insulin and safely dispose of injection devices At study entry, patients receive a 3-month supply of BD Micro-Fine Plus 4 mm 32G injection pen needles, depending on the type of their injection therapy, in order to secure their single use, as well as access to on-line education. Moreover, patients receive an extra package of BD Micro-Fine Plus 4 mm 32G injection pen needles (100 items per package) to cover losses or other contingencies (Table 3).

At visit No. 3 patients will receive another 3-month supply of BD Micro-Fine Plus 4 mm 32G injection pen needles.

Table 3.

Total number of injections per day	Number of packages (3-month supply), given that each needle is used only once	Number of packages to cover losses or other contingencies	Total number of packages per patient
1	1	1	2
2	2	1	3
3	3	1	4
4	4	1	5
5	5	1	6
6	6	1	7

Depending on patient's condition, insulin TDD and other factors, the physician can recommend that the patient reduces insulin TDD after visit № 1.

The physician must recommend to the patient not to change the insulin preparations (for intermediate- and long-acting insulins) and/or the insulin subgroup (for short- and ultra short-acting insulins) throughout the period of the patient's participation in the study.

7.7.Patient safety

The trial will be carried out in accordance with Russian law, the regulatory requirements for quality clinical studies, and the WMA Declaration of Helsinki in so far as relevant to research ethics. Patients will be entitled to forego participation or pull out of the study for any reason and at any stage, which will not affect the quality or availability of their health care.

Participation in the study does not put patients at any significant risk, but encourages them to adopt the correct injection technique, including the avoidance of insulin injection in lipohypertrophic areas. Patients who stop injecting insulin in lipohypertrophic areas and start to inject into healthy tissue often note the necessity to reduce insulin TDD (sometimes up to 20%) in order to avoid hypoglycemia. This information is made available to the investigators, who instruct patients accordingly.

Strict confidentiality is guaranteed for all patients. Patients are not paid for their participation in the study; however, during the study, the Sponsor provides the participants free

of charge with a sufficient supply of BD Micro-Fine Plus 4 mm 32G needles for pen injectors. Also, the Sponsor provides the participants free of charge blood glucose meters, with sufficient amount of strips and lancets. Blood glucose meters must be returned to the sites by the patients on the 6 months follow up (completion) visit.

8. Monitoring plan

Clinical monitoring of this clinical trial will be carried out by the Sponsor, the «Becton Dickinson and Company», Russia. Study monitoring will be conducted by a clinical monitor with an appropriate background and experience. The duties of the clinical monitor include the maintenance of regular contacts with every research center by phone and/or during personal visits to the research center to make sure that:

- The study is carried out in accordance with the requirements of GOST R ISO 14155-2014 [6];
- Study design is adhered to;
- Complete, timely and accurate data are provided;
- Problems with discordant or incomplete data are being solved;
- Cases of complications and unforeseen undesirable effects are brought to the attention of the Sponsor and the research center ethics committee;
- Technical abilities of the research center keep complying with the study requirements.

The clinical monitor will start the conduct of the study in the research center during the site initiation visit or in the course of the study activation visit, and continue the monitoring visits to the research center at the required frequency. The first monitoring visit can usually be made immediately after the start of a patient's enrollment. At this visit and all other monitoring visits, the clinical monitor will compare data entered in the eCRF with that from the medical documents (primary documents) in the center. The primary documents include the medical card, the filled in laboratory analysis form, physician's notes, the patient's medical history, recorded data from automated instruments or any other documents prepared and supported by the investigator/medical staff or support services which contain records of patient monitoring and other data pertaining to the trial. For the purpose of confirming the correctness of the obtained informed consent, adherence to the protocol requirements, the adequacy of reporting adverse events (AE) and subsequent AE follow-up, and information about procedures, the primary documents must be available to the clinical monitor and kept at the research center. Data from the analysis of the eCRF and the primary documents will be discussed with the investigator during the monitoring visits. The dates of the monitoring visits will be entered in the registration book (Appendix A) kept at the research center. The Sponsor assumes that during the monitoring visits the principal investigator and investigator must be available for contacts, the primary documents must be available for viewing, and the required site conditions provided for the assessment of documents pertaining to the trial.

The research centers must get in touch with all patients, making every endeavor to make sure that they turn up for consequent follow up visits. The research centers must have log books with records of patient contact dates and the results of such contacts. After 3 unsuccessful attempts of contact (e.g., by phone or e-mail) to arrange a patient's visit, the patient will be considered as lost to subsequent follow-up.

8.1. Electronic data capture and storage.

Data management will be carried out by Becton, Dickinson and Company in the United States of America. Data will be collected electronically, and electronically entered records present on the website will be entered directly into the controlled database. Data safety is secured by password protection, restricted access, control books and regular data backup. Upon completion of the data investigation and verification, the data will be checked for accuracy and completeness, after which the database will be blocked to prevent any additional modification. A copy of the blocked database will be passed on to the BD Corporate Statistics Department (USA) for statistical analysis.

Electronic data collection in the eCRF is based on the use of Oracle software, and is developed, supported and allocated by Becton, Dickinson and Company in the United States of America..

8.2. Patient identification

In order to rule out a prejudiced attitude and preconception, each patient will be assigned a participant identification code which is filled in the individual registration card (IRC) and study participant information sheet. The code consists of six digits, which designate the following:

- , the first three digits are the number of the research center, e.g. 001, 002, 003 etc., which will be assigned in the course of a trial depending on the time of the study entry of each center, and the other three digits indicate the consecutive number of the study participant in a given center.

9. Investigator's range of responsibilities

All research centers will have to sign an agreement with the Sponsor. All principal investigators and investigators will undergo training in study protocol, data entry in the electronic database and the use of disposable BD Micro-Fine Plus: 32G (0.23 x 4 mm) needles for the pen injector.

10. Statistical analysis

It is of the utmost importance that patients invited to participate in the study comprise a representative sample of Russian patients receiving insulin injections. For this reason, the chosen eligibility criteria are as comprehensive as possible.

10.1. Projected sample size

Based on data observed in internal studies with similar designs, assuming an HbA1c decrease of 0.4% between baseline and 6 months and a standard deviation of paired differences of 1.2%, a sample size of 73 subjects would be needed to demonstrate statistical significance using a one sample t-test with a power of 80% and alpha equal to 0.05.

10.2. Statistical analysis plan

For descriptive statistics and conclusive statistics, R 3.4.4 or more recent version and Rstudio will be used. The HbA1c and insulin total daily dose will be analyzed using linear models with mixed effects (with transformation or without it, whenever necessary) where

lipohypertrophy will be a fixed effect. Analyses will be done overall and per lipohypertrophy sub-group (with or without LH) whenever the sub-group effect is significant.. Generalized linear models with mixed effects will include logistic models for binomial responses or Poisson models for count responses.

Fixed effect models can be used when models with mixed effects cannot be employed. The effect of different covariates will be studied (including, but not limited to these), such as site, age, BMI, gender and diabetes type, as well as their interaction. The threshold to keep covariates in a model will be $p < 0.05$.

Non-parametric tests will be used if basic assumptions do not hold for the models.

McNemar's test will be used, when necessary, for contingency tables.

Statistical methods will be detailed in a Statistical Analysis Plan. Additional analyses may be performed and will be defined in the Statistical Analysis Plan.

11. Data management

All documents containing personal information of the study participants must be stored at the trial conduct site.

The data collected during the course of the study will be entered in the eCRF. The study participants will be identified by the study participant code which is generated by the eCRF. Patient confidentiality will be maintained throughout the study, including the publication of the study results. The principal investigator or sub-investigator will review and sign each form (eCRF, AE), the system will record the date when it was signed. The investigator's signature is the confirmation that clinical and laboratory data entered in the form are complete, accurate and veracious.

The data obtained and entered in the eCRF are the property of Becton, Dickinson and Company.

The study data, copies of the study materials and the medical documents will be provided to the Ethics Committee of the research center, the authorized bodies for internal audit should it be conducted, and on the audit demand. All data obtained in the course of the study will be stored confidentially for at least 3 years after the end of this trial.

12. Appendices to the clinical trial protocol

In case of the introduction of amendments or additions to the protocol, an amended protocol of the clinical trial will be created, which will be assigned a new version number. A list of introduced amendments and additions indicating their containing pages will be attached to the amended protocol. The protocol will be used in the study only after its approval by the Ethics Committee of the research center.

13. Adverse events, unfavorable effects of the device and its disadvantages

In this study, the Sponsor does not anticipate the occurrence of adverse events, except for those listed in paragraph 5 of this protocol.

All adverse events (defined below) are recorded, and serious adverse events (defined below) are reported to the principal investigator, the Ethics Committee and the Sponsor.

Adverse event (AE) is any unfavorable and involuntary event (including non-typical data of laboratory investigation), symptom or disease diagnosed in a subject and associated with his/her participation in the study. Such events imply the ones which were not seen at the baseline and/or deteriorated as compared with the baseline level. An undesirable event does not necessarily have to be causally related to the patient's participation in the study.

Serious adverse event (SAE) is an unfavorable event occurring in the course of study which leads to any of the following outcomes:

- a) a lethal outcome;
- b) a serious deterioration of the health of the subject, which, in turn, leads to either:
 - 1) disease or a life-threatening injury, or
 - 2) injury, or
 - 3) hospitalization or its extension, or
 - 4) medical or surgical intervention for the prevention of the life-threatening disease or injury;
- c) a fetal injury, fetal death or abnormalities or defects of fetal development.

All AE (related and unrelated to injections) which meet the criteria for SAE must be immediately reported to the Sponsor and LEC, followed by filling in forms provided by the Sponsor to give a full description of the course of the event, the treatment conducted, and the final outcome. The first SAE reporting to the Sponsor must be carried out not later than two (2) working days after the Principal investigator has become aware of the event.

Unanticipated serious adverse device effect (USADE) is any serious undesirable and unanticipated effect on the state of health state or safety of the patient, or any life-threatening problem or death caused by or related to the injection needle if this event, problem or death has not been mentioned in the study design or in the application to conduct a research study (including additional plan or application) with an indication of its nature, severity or frequency of occurrence, or any other unforeseen serious problem related to the device and pertaining to the rights, safety or wellbeing of the patients.

Any USADE will be immediately reported to the Sponsor and LEC. That said, this report must be received by the Sponsor and LEC not later than two (2) working days from the moment when the Principal investigator has become aware of it.

In case of an occurrence of a SAE or USADE, the patient must contact the Principal investigator or investigator, whose contact phone numbers are given in the patient information leaflet.

13.1. Adverse Event (AE) Management

At each study contact, subjects will be questioned in an open-ended manner regarding any new or worsening undesirable signs or symptoms they may have experienced since the previous contact. Elicited signs and symptoms must be comprehensively documented on the appropriate source documentation.

Each sign, symptom, disease or illness reported must be evaluated by the Investigator or designee to determine if it meets the definition of an Adverse Event.

The clinical course of the event will be followed according to accepted standards of medical practice until the event resolves, stabilizes, or in the opinion of the Investigator, is no longer considered clinically significant. The Investigator must supply the Sponsor with information concerning the follow up and/or resolution of the AE.

Some reported or observed signs and symptoms are inherent to subcutaneous injection and are likely to occur transiently for nearly all subjects in this study. Such signs or symptoms will **not** be considered AEs as long as they are mild (transient, easily tolerated, no interference with daily activities) and the Principal Investigator agrees. The following will not be **not** be considered AEs:

- Mild, self-limited pain, swelling at the injection site
- Mild bruising at the injection site
- Mild self-limited bleeding at the injection site

However, these signs and symptoms **must be considered AEs and** documented on the Adverse Event eCRF should any of them occur in such a way that the extent or nature of the experience exceeds that normally associated with the procedure, as judged by the Subject to be excessive pain, bruising or bleeding.

Some signs and symptoms are inherent to the conditions under study (i.e. diabetes) and are likely to occur transiently for nearly all subjects in this study. Episodes of hyperglycemia and hypoglycemia occurring after subject enrollment and exposure to study product and/or study procedures, should be reported based on the following criteria:

- All blood glucose values <2.8 mmol/L (hypoglycemia) or >22.2 mmol/L (hyperglycemia) that require 3rd party (defined as, assistance of another person to administer carbohydrates or glucagon) or medical assistance for recovery will be recorded as an AE and assessed for seriousness.
- Any self-identified hypoglycemia or hyperglycemia without a BG reading or with any BG reading that requires 3rd party or medical assistance for recovery will be recorded as an AE and assessed for seriousness.
- All blood glucose values >22.2 mmol/L (and no symptoms of ketosis) will not be considered an AE.
 - Signs of ketosis are elevated BG along with nausea but individual has the ability to drink fluids and nausea is resolved with additional insulin and oral fluids, this may be considered an AE per the discretion of the PI or designee.

All blood glucose values <2.8 mmol/L, or self-identified as hypoglycemia that resolves with standard carbohydrate administration will not be recorded as an AE unless otherwise determined by the Principal Investigator. However, these signs and symptoms **must be considered AEs and** documented on the Adverse Event eCRF should any of them occur in such a way that the extent or nature of the experience exceeds that normally associated with the procedure, as judged by the PI, or the event meets the criteria for a Serious Adverse Event (SAE).

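### Protocol 13.1 gives opposite AE instructions for glucose above 22.2 mmol/L without ketosis symptoms when medical assistance is needed

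*Protocol*

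**What the plan says.** Protocol 13.1 (Adverse Event (AE) Management) has a block on signs and symptoms that belong to diabetes itself, with criteria for reporting hyperglycemia and hypoglycemia.

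- **Bullet 1** covers values below 2.8 or above 22.2 mmol/L that need the help of a third party or medical assistance. Third-party help is defined as another person's assistance to "administer carbohydrates or glucagon) or medical assistance for recovery will be recorded as an AE and assessed for seriousness".
- **Bullet 2** applies the same instruction to "Any self-identified hypoglycemia or hyperglycemia without a BG reading or with any BG reading that requires 3rd party or medical assistance for recovery".
- **Bullet 3** reads "All blood glucose values >22.2 mmol/L (and no symptoms of ketosis) will not be considered an AE".
- **The sub-bullet to bullet 3** describes ketosis signs where the "individual has the ability to drink fluids and nausea is resolved with additional insulin and oral fluids", and leaves AE status to the discretion of the PI or a designee.
- **The hypoglycemia exclusion** that follows covers values below 2.8 mmol/L, or an event "self-identified as hypoglycemia that resolves with standard carbohydrate administration will not be recorded as an AE", unless the PI decides otherwise.
- **The closing sentence** restores AE status if "the extent or nature of the experience exceeds that normally associated with the procedure, as judged by the PI", or if the event meets the SAE criteria.

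On the analysis side, SAP section 7 (Safety Analysis) plans a listing of AEs and nothing more. SAP 5.2.5 summarizes five categories of hypoglycemia; there is no counterpart for hyperglycemia.

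**The concern.** Bullets 1 and 3 use the same threshold and both claim to cover all values above it. Bullet 1 turns on assistance and ignores ketosis; bullet 3 turns on ketosis and ignores assistance. Where assistance was needed and ketosis symptoms were absent, one says to record and the other says not to. A center that applies bullet 3 literally is following the protocol, and so is a center that applies bullet 1.

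What is at stake is the completeness of the AE listing and its consistency between centers. Protocol 13.2 requires severity, relationship and action taken for AEs, so an event classed as not an AE escapes that assessment. The meter download may hold the glucose value, but it does not show that help was needed. Among the planned outputs, only the AE listing would show that for hyperglycemia. The direction is relevant in this trial because Protocol 7.6 lets the physician recommend a lower insulin dose after visit 1, and 7.7 mentions reductions of up to 20%. The link from there to hyperglycemia is my inference; the protocol does not state it.

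**Working it through.** No formula applies and the plan gives no figure to reproduce. The check is to apply each rule in 13.1 to every combination of assistance and ketosis symptoms for glucose above 22.2 mmol/L.

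| Case | Assistance needed | Ketosis symptoms | Rules that apply | Instruction | Conflict |
|---|---|---|---|---|---|
| 1 | No | No | Bullet 3 | Not an AE | No |
| 2 | No | Yes | Sub-bullet | PI or designee discretion | No |
| 3 | Yes | No | Bullet 1 (and 2 if self-identified) against bullet 3 | AE and not an AE | **Yes** |
| 4 | Yes | Yes | Bullet 1 (and 2 if self-identified); bullet 3 does not apply | AE | No clear conflict |

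As written, 1 of 4 combinations receives opposite instructions. If bullet 3 is limited to readings that needed no assistance, case 3 is governed by bullets 1 and 2 alone and the count is 0 of 4. These are counts of rules, not of patients.

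**Which kind of assistance.** Third-party help is defined through carbohydrates or glucagon, which treat low glucose. For hyperglycemia, case 3 therefore arises mainly through medical assistance.

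**Comparison with the hypoglycemia exclusion.** That exclusion is limited to events that resolve with standard carbohydrate and lets the PI decide otherwise. Bullet 3 carries neither limit in its own wording.

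**What the safeguards recover within case 3.**

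- Serious events: Protocol section 13 states "All AE (related and unrelated to injections) which meet the criteria for SAE must be immediately reported to the Sponsor and LEC", and hospitalization or intervention to prevent a life-threatening condition counts as serious. The closing sentence of 13.1 also restores events that meet the SAE criteria.
- Non-serious events: only the PI-judgment limb of that closing sentence remains. It follows directly on a sentence about hypoglycemia and measures the event against what is normal for the procedure, so its reach to hyperglycemia is uncertain. Even where it applies, it puts judgment in place of a mandatory rule.

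**How many events.** The documents give no rate for assisted hyperglycemia, so no count can be computed. At most 90 patients are followed for 6 months, and Protocol 7.3 excludes those at high risk for ketoacidosis and/or hyperglycemia. An affected event must also miss every SAE criterion and not be restored by the PI.

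**The case against.** The strongest reply is that the bullets have one sensible reading. If bullet 3 overrode bullet 1, the hyperglycemia half of bullet 1 would operate only when ketosis symptoms were present, and part of bullet 2 would be cancelled by the line after it. Reading bullet 3 as covering high readings alone gives every bullet something to do. I agree that this is probably the intent. The text does not say so, however, and centers should not have to infer it.

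Second, the PI override may well reach hyperglycemia. Its wording echoes the opening of the block, which introduces both conditions, and the injection-site block earlier in 13.1 has the same structure, with a closing sentence that covers the whole block. This is plausible, but the outcome still rests on individual judgment at each center.

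Third, other procedures make silent loss less likely. Signs and symptoms elicited at each contact go into source documents and are assessed against the AE definition (13.1), patients note adverse effects in the diary (7.5), and the monitor compares the eCRF with source (section 8). These help, but none settles which bullet applies, so a monitor has no clear rule for deciding whether an AE entry is missing.

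Fourth, the affected group may be empty, and inconsistent recording between centers is a risk rather than a demonstrated effect. Both points stand, and they set the severity.

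Finally, case 4 has a possible overlap: nausea that resolves with insulin given by medical staff would be mandatory under bullet 1 and discretionary under the sub-bullet. The sub-bullet does not mention assistance, so I do not count this as a clear conflict, but amending bullet 3 alone would leave it in place.

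**Conclusion.** The inconsistency is real and follows from the wording alone: for one of four combinations above 22.2 mmol/L, Protocol 13.1 both requires and rules out an AE record. Confidence in the textual conflict is high. Its practical effect is confined to non-serious, medically assisted hyperglycemia without ketosis symptoms. That effect is probably small and cannot be quantified from the documents. It concerns the AE listing only; the HbA1c analysis, the sample size and the SAP models do not depend on it. Severity is minor. The conclusion assumes that centers may apply bullet 3 as written; if all of them adopt the probable intent, no event is lost.

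**What to change.** Let the assistance rule govern. Amend bullet 3 so that a value above 22.2 mmol/L is excluded from AE recording only when there are no ketosis symptoms *and* neither third-party nor medical assistance was needed for recovery. Ordinary high readings stay excluded, and the bullet gains a limit comparable to the one already on the hypoglycemia exclusion. If the sponsor also wants to remove the possible overlap in case 4, the same condition can be added to the ketosis sub-bullet.

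The cost is one clause in Protocol 13.1. Under Protocol section 12 an amended protocol needs a new version number and ethics committee approval before use, so the change can go into the next amendment. Endpoints, sample size and SAP models stay as they are.
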